We propose to recruit a prospective cohort of persons with TBI to compare effects of Bright White Light exposure to Red Light (RL) exposure. Light therapy treatments will be given daily in the morning for up to 10 days, and an Actiwatch will be worn that records movements for the entirety of the study. We will utilize objective assessments of sleep quality, subjective mood report, rate sleepiness and fatigue and complete measures of attention and participation in rehabilitation therapies to explore the

effects of light exposure in the acute inpatient rehabilitation setting. We will also evaluate the anticipated device costs and staff burden involved in utilizing light therapy exposure in the inpatient rehabilitation clinical setting. An overview of study procedures with timeline is described in Figure 1 below with further details in the sections that follow.

Figure 1. Overview of Study Procedures for TWILIGHT

VI. Screening for Eligibility:

Although subjects will be screened for this study concurrent with screening for eligibility for enrollment into the Traumatic Brain Injury Model System (TBIMS) study (Traumatic Brain Injury Model Systems, 2013), these are independent studies and subjects will have the choice to enroll in both, neither, or either one. The TBI Model Systems program, sponsored by the National Institute on Disability and Rehabilitation Research (NIDRR), is the largest longitudinal study of TBI in the nation. NIDRR awards 5 year grant awards to institutions that are national leaders in medical research and patient care and these. Institutions which receive this distinction are collectively termed, the TBI Model Systems. As part of the TBI Model Systems, the University of Washington TBI Model Systems research team is recognized as providing the highest level of comprehensive specialty services from the point of injury through chronic care stages, including re-entry into full community life. The current grant cycle is for the 2012-2017 time period, and one of the areas of interest for the UW TBI Model Systems research team is the treatment of sleep difficulties after TBI.

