5. Past medical history of narcolepsy
6. Past medical history of bipolar disorder
7. Past medical history of obstructive sleep apnea (OSA)
8. Sleep disturbance defined as having a "0" rating by research staff (using all sources available). If rated a "0" for no sleep disturbance, they must also NOT be receiving sleep medications in the last 72 hours
9. Suspected diagnosis of obstructive sleep apnea (determined by the Berlin Questionnaire)
10. Tetraplegia with less than antigravity strength in all myotomes caudal to C6 level given the limitations on measuring movements with actigraphy in this population (i.e. cannot reliably detect upper extremity or lower extremity movement with this level of paralysis).
11. Current medical orders indicated for night time sleep disruption (e.g. chest PT, MIE q2 hours of meds that disrupt sleep). *May be re-approached if the medical orders are no longer in place.

IX. Rationale for Study Population

The study population of interest is TBI in the setting of acute inpatient rehabilitation, which is typically moderate to severe TBI. Persons less than 18 years of age or greater than 70 years are being excluded from the study because of baseline sleep physiology differences seen in younger and advanced ages. We wish to enroll those with sleep disturbances; those with normal sleep will not be enrolled. We are excluding those who would not benefit from light exposure due to eye abnormalities or those with other pathology that will interfere with sleep and cannot be affected by light exposure. Additionally, since actigraphy relies on limb movement for recording, those with tetraplegia would be excluded.

X. Data Collection and Measures

Screening of subjects will need to occur to determine eligibility of subjects, including review of medical chart. If patients are not eligible or are excluded based on exclusion criteria, no identifiable data is retained. Once consented into the study, the exclusion criteria will be reviewed with the patient and/or their legal representative. Data collection measures, areas assessed, and the timing of when this data is collected is shown in Table 1.

Table 1: Data Collection Measures and Areas Assessed

Measure	Area to be Assessed	Screening and Baseline (Day 0-2)	Intervention (Days 3-12)	Outcome (Day 13)
Demographics	Characteristics (age, education, gender)	X		
Injury characteristics	Cause of injury, date of injury, lowest GCS, PTA/GOAT	X		

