Medical History	Diagnoses, medications at enrollment, symptoms, associated injuries (ICD-9 codes), vital signs	X		
Berlin questionnaire	Sleep apnea	X		
Clinician Rating: Delirium Rating Scale Revised 98 Item 1	Sleep disturbance	X		
Makley scale	Sleep disturbance	X	X	
Actigraphy	Sleep parameters	X	X	
Light Therapy Time	Light exposure time		X	
Medication categories	Potential confounders (see data sheet)	X		X
FIM™ Scores and Efficiency	Functional score	X		X
Hospitalization	Acute LOS, Rehab LOS	X		X
Symbol Digit Modalities Test	Attention	X		X
PANAS	Mood	X		X
Therapy participation	Function	X		X
Karolinska Sleepiness Scale	Daytime sleepiness	X		X
Barrow Neurological Institute Fatigue Scale	Daytime fatigue	X		X

A. Screening Measures:

The following data will be used as descriptive characteristics of the subjects upon study completion. Initially this data will be used during the screening process to ensure appropriate patients are approached for participation:

- **Demographics:** Age, gender, race/ethnicity, weight (kg), height (cm), BMI (calculated).

- **Injury Characteristics:** Time since injury, Post-resuscitation GCS score, duration of PTA as measured by TBIMS procedures using the Galveston Orientation and Amnesia Test (GOAT), associated injuries including ICD codes.
- **Medical History:** Current diagnoses, past diagnoses, medications (at enrollment, during treatment and at outcome measure), vital signs.
- **Berlin Questionnaire** (Netzer NC, 1999): The 10-item questionnaire consists of 3 categories related to the risk of having sleep apnea. Patients can be classified into High Risk or Low Risk based on their responses to the individual items and their overall scores in the symptom categories.

B. Randomization Measure:

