Randomization will occur by research staff member assessing the patient for sleep disturbance, using all sources available, in the first item question from the *Clinician Rating: Delirium Rating Scale – Revised 98* (DelRS-R98) (Trzepacz PT, 2001). Our recent prevalence work showed that 86% of acute TBI admissions have sleep abnormalities using clinician ratings, specifically the DelRS-R98 (Nakase-Richardson R S. M., Prospective evaluation of the nature, course, and impact of acute sleep abnormality following TBI, 2013). Sleep disturbance questions will be asked of the clinical staff whom were involved in caring for the patient during Day 1 of study participation, significant other (if available), and directly of the patient (if possible). The rating will be used as a sleep disturbance severity marker which will be utilized by the statistician during randomization to help control for sleep disturbance severity (Sjösten N, July 2009).

C. Primary Outcome Measure:

Sleep efficiency scores derived from actigraphy data will be the primary outcome, and analysis will be done by [name] at the University of Washington. An Actiwatch 2 (Philips/Respironics, Bend, OR) will be used for study purposes to facilitate consistent measurement across sites. We will set the Actiwatch to record activity data in 60-second intervals. Actigraphy data will be automatically scored with Actiware software (Respironics, Philips Healthcare), which uses validated algorithms to determine whether an epoch of activity is “sleep” or “wake” (Cole RJ, 1992). Typically there is a lack of a consistent sleep/wake cycle in the study population, therefore we will be using sleep efficiency and total sleep time scores obtained during a set night-time interval (2200 to 0600) as the primary index of sleep function, as has been used in previous publications[39, 40]. We will be comparing average between group differences between the BWL and RL groups at baseline and after 10 days of light exposure.

D. Secondary Outcome Measures:

- **Makley Scale:** The Makley scale is a 4-point ordinal scale which allows staff to score sleep as follows: 0 = asleep; 1 = drowsy/falling asleep; 2 = drowsy/waking up; 3 = awake. An hourly sleep log on each patient will be filled out every two hours by the unit nursing staff from 2200 to 0600 hours starting at baseline and through the duration of the study.[41]

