Day 0-1 (2 days): After determining eligibility, the participant will be fitted with an Actiwatch (actigraphy) for continuous monitoring of activity levels both during the day and night (American Sleep Disorders Association, 1995). The Actiwatch will be worn continuously (with removal as needed for hygiene, shower or other clinical care) from enrollment to outcome measurement. Actiwatches will be fully charged and cleared of all previous data before being provided to a subject. Units will be set to record activity data in 60-second epochs. Actiwatches have sufficient built-in memory capacity and battery life to be used for approximately 30 days without recharging. Additionally, sleep logs that rate patient sleep are filled out every hour, between the hours of 2200-0600, this information is then obtained

as completion of the Makley scale. A complete review of symptoms and medical history will be obtained from the subject, LAR, and medical records.

Day 2: Baseline data collection is obtained (See Appendix for Baseline Data Collection Forms). Measures collected include: Symbol Digit Modalities Test, Positive and Negative Affect Schedule (PANAS), Barrow Neurological Fatigue Scale. Clinical Staff, will be asked if there was sleep difficulties and therapist will be asked to rate therapy participation for that day.

Day 2: Randomization. After baseline testing is completed, subjects will be randomized (50:50) using a 2-level stratification design based on two pieces of information:

- 1) Center (U. Washington-Seattle, Baylor-Dallas, Mount Sinai-New York) and
- 2) Severity of Sleep Disturbance using Delirium Rating Scale-Revised 98 Item 1

The rating for the Delirium Rating Scale Item 1 are: 1=Mild, 2=Moderate, 3=Severe

(Nakase-Richardson R S. M., Prospective evaluation of the nature, course, and impact of acute sleep abnormality following TBI , 2013) Using an Access Database, developed by [name] at the University of Washington, centers will randomize the participant into either the Bright White Light Group or the Dim Red Light Group. [46]

Light Therapy:

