- 3) Clinical Staff feedback: phototherapy intervention will rated using a likert scale on the following categories:

- a. Ease of use
- b. Perceived relevance to rehabilitation care
- c. Impression of effectiveness.

Post Light Therapy Outcome Assessment

Day 13: At the conclusion of the light therapy sessions (and prior to discharge from rehabilitation), a blinded Outcomes Examiner will complete the post therapy outcome assessment. This assessment will include the following:

- Symbol Digit Modalities Test
- Positive and Negative Affect Schedule (PANAS)
- Barrow Neurological Fatigue Scale

XII. Data Analysis

The primary outcome is the between-group difference (BWL vs. RL exposure) in average sleep efficiency at baseline compared to after 10 days of light treatment. ANOVA will be used to compare groups controlling for demographics, injury severity, and use of medications.

Secondary outcomes (mood, therapy participation, attention, daytime sleepiness/fatigue) between groups assessed at baseline and after 10 days of light therapy will be compared using repeated measures ANOVA. FIMTM efficiency and inpatient rehabilitation length of stay will also be compared between groups using ANOVA controlling for the same variables as the primary outcome. Descriptive analysis will summarize responses to the nursing burden questions including estimated staff time for the intervention.

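### The primary analysis of sleep efficiency should adjust for baseline sleep efficiency, and the nights that form each average should be named

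*Combined protocol and SAP*

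**What the plan says.** Section X.C fixes the clock window within each night (2200 to 0600) and says the comparison will be of "average between group differences between the BWL and RL groups at baseline and after 10 days of light exposure". Section XII repeats the contrast as the group difference "in average sleep efficiency at baseline compared to after 10 days of light treatment" and gives the model: "ANOVA will be used to compare groups controlling for demographics, injury severity, and use of medications". Baseline sleep efficiency is not in that list. Secondary outcomes measured at both times are assigned a repeated measures ANOVA; the primary outcome is assigned an ANOVA.

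Neither section names the nights, or their number, in the baseline or the follow-up average. Section XII notes that the software returns a value for each night and a mean over all nights, and does not choose between them. Section XIII, Table 2, lists an actigraphic data handling plan among the pre-enrollment tasks; that plan is not in the documents.

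On timing:

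- The Table 1 treatment column is headed "Intervention (Days 3-12", with outcome on Day 13. Actigraphy is ticked at baseline and during the intervention, not at Day 13.
- Section XI starts actigraphy on Days 0-1, randomizes on Day 2, and has the watch worn "from enrollment to outcome measurement". It heads the light sessions Days 3 to 13 but specifies ten of them.
- Section XV ends adverse-event follow-up on Day 15, described as two days after the last treatment.

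**The concern.** Two gaps affect the primary result.

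First, a patient's own earlier sleep efficiency is likely to be a strong predictor of later sleep efficiency, and the trial already collects it before allocation. Read literally, the model either ignores it (post-only comparison) or uses it only by subtraction (change score, or the equivalent group-by-time test with two time points). Both leave precision unused.

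Second, the night after session ten, the last few nights and all treatment nights are each a fair reading of the follow-up average. They are different endpoints: a single night is noisy, while a mean over all treatment nights dilutes an effect that builds up. Baseline could be two nights (Section XI) or three (Table 1, Days 0-2).

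**Working it through.** **The plan's own figure.** Section VII assumes an effect size of 0.5 and 80% power. A two-sample t-test at two-sided 0.05 (assumed, since alpha is not stated) needs 63.77, so 64 per group and 128 in total. This matches the plan. The 0.5 was set below a 0.63 reported for sleep duration, so it is tied to no particular sleep-efficiency window.

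**Days and nights.** Session n falls on Day n + 2, so session 10 is Day 12. Days 3-12 are 10 mornings and Days 3-13 are 11. Section XV gives 15 − 2 = Day 13, whereas Table 1 gives 12 + 2 = Day 14 for the end of follow-up. If the watch comes off at the Day 13 assessment, a Day 12 last session leaves one recorded night after all ten sessions (night 12/13).

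**Why a covariate cannot do worse.** Let v1 and v0 be the variances of the follow-up and baseline means, and C their covariance.

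- ANCOVA residual variance: v1 − C²/v0
- Change-score variance: v1 + v0 − 2C
- Post-only variance: v1

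Change score minus ANCOVA is (v0 − C)²/v0, and post-only minus ANCOVA is C²/v0. Neither can be negative. Apart from one degree of freedom, ANCOVA is at least as precise whatever the ICC.

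**Size, under assumptions not in the documents.** Take a night-to-night ICC of 0.3 to 0.6, independent night errors, b = 2 baseline nights and k = 3 follow-up nights. Let f (0 or 0.2) be extra occasion-specific patient variance at each time, as a share of the ICC, so that true change has variance 2·ICC·f. Then v1 = ICC(1+f) + (1−ICC)/k, v0 = ICC(1+f) + (1−ICC)/b and C = ICC.

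| ICC | f | v1 | v0 | ANCOVA | Change | Change/ANCOVA | Post-only/ANCOVA |
|---|---|---|---|---|---|---|---|
| 0.3 | 0 | 0.533 | 0.650 | 0.395 | 0.583 | 1.48 | 1.35 |
| 0.3 | 0.2 | 0.593 | 0.710 | 0.467 | 0.703 | 1.51 | 1.27 |
| 0.6 | 0 | 0.733 | 0.800 | 0.283 | 0.333 | 1.18 | 2.59 |
| 0.6 | 0.2 | 0.853 | 0.920 | 0.462 | 0.573 | 1.24 | 1.85 |

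First row: 0.3 + 0.7/3 = 0.533; 0.3 + 0.7/2 = 0.650; 0.533 − 0.09/0.650 = 0.395; 0.533 + 0.650 − 0.6 = 0.583. In patient numbers, 128 analysed by change score carry the precision of about 128/1.51 = 85 to 128/1.18 = 108 analysed by ANCOVA.

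**Correlated nights.** With an assumed lag-1 correlation of 0.5 between neighbouring nights and f = 0, the error term for three nights is multiplied by (3 + 4×0.5 + 2×0.25)/9 = 0.611 and for two nights by (2 + 2×0.5)/4 = 0.75. At ICC 0.3, v1 = 0.728 and v0 = 0.825, so the ratio is 0.953/0.619 = 1.54. At ICC 0.6, v1 = 0.844 and v0 = 0.900, so it is 0.544/0.444 = 1.23. The change-score range hardly moves.

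**Window, as illustration only.** Under the table's assumptions, one night has 1.6 to 2.2 times the ANCOVA residual variance of a three-night mean. If the effect rises linearly from 0.1 to 1.0 over ten nights, the last three average (0.8 + 0.9 + 1.0)/3 = 0.90 of the final-night effect and all ten average 0.55. If 0.5 describes the three-night mean, one-night power at 64 per group is 48-61% with a constant effect or 56-70% with build-up; for all ten nights it is 88-96% or 48-61%.

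**The case against.** The strongest reply is that the window may already be fixed. The actigraphic data handling plan is a pre-enrollment deliverable and is the natural place for such a rule. This stands. A reader might infer that the sponsor is free to choose the window after seeing the data; the documents do not show that. In simulation, type I error reaches 8-9% only if someone takes the better of a one-night and a ten-night analysis, and nothing in the plan suggests it.

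A second reply is that baseline is already part of the contrast, and that randomization is stratified by rated sleep disturbance. The first half is right: the natural reading is a change or group-by-time comparison, so it would be too strong to say that baseline is ignored. The change-score ratio is therefore the relevant one, and the post-only ratio describes a less natural reading. Stratification helps balance, but the rating is not in the listed covariates either, and balance alone does not remove the variance that a measured baseline explains.

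Third, the date conflict might be read as leaving no night after session ten. Table 1 and the count of ten daily sessions from Day 3 both support Day 12, so that reading is weak. On a Day 12 finish, Section XV merely adds a day of safety follow-up.

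Finally, the power figures might be read as showing an underpowered trial. They rest on assumed correlations and show only that the windows differ. With a lag-1 correlation of 0.3 to 0.5 between nights (also assumed), the one-night to three-night variance ratio falls to about 1.25 to 1.7.

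**Conclusion.** The concern holds as a precision and specification point. The listed primary model omits a baseline measure that the trial already collects, and neither average has named nights. That ANCOVA is at least as precise follows from algebra. The size of the gain, a variance 1.2 to 1.5 times larger with a change score, rests on an assumed ICC of 0.3 to 0.6, independent nights, two baseline nights and a three-night follow-up mean. The unnamed window is missing detail that the unseen handling plan may supply. The conflict over the last session is a one-day slip. None of this shows that the comparison is biased or that the sample size is wrong.

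**What to change.** 1. In Section XII, analyse the follow-up mean by ANCOVA, adding the mean sleep efficiency of nights 0/1 and 1/2 to the existing covariates. Both nights precede the Day 2 randomization, provided the watch goes on by the evening of Day 0. Night 2/3 follows randomization but precedes treatment and may be added if stated; leaving it out forgoes a 5-14% reduction in residual variance under the assumptions above.
2. In Sections X.C and XII, name one multi-night follow-up window before unblinding, for example the mean over nights 10/11, 11/12 and 12/13 (after sessions 8, 9 and 10). If the handling plan already sets a window, copy that one instead.
3. State Day 12 as the last session. Change Section XI to Days 3-12, and Section XV to Day 14 or to Day 15 described as three days.

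Do not substitute a patient's last recorded nights when discharge comes before the window. That would mix different amounts of light exposure, and length of stay is itself a hypothesized treatment outcome (Hypothesis 2), so the substitution could bias the comparison.

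The cost is a dated amendment before unblinding, since the primary model and endpoint definition change. No new data are needed. Under a linear build-up, the three-night mean gives up about 10% of the final-night effect.

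### The primary ANOVA in Section XII does not use baseline sleep efficiency as a covariate and omits the randomisation strata; an ANCOVA with these terms would usually be more precise at almost no cost

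*Combined protocol and SAP*

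**What the plan says.** **Primary analysis.** Section XII gives the primary outcome as a between-group difference in "average sleep efficiency at baseline compared to after 10 days of light treatment" and then says "ANOVA will be used to compare groups controlling for demographics, injury severity, and use of medications". Section X.C words the comparison differently: "We will be comparing average between group differences between the BWL and RL groups at baseline and after 10 days of light exposure". Neither says whether the analysed variable is the change from baseline or the post-treatment value.

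**Other outcomes.** In Section XII the secondary scales "assessed at baseline and after 10 days of light therapy will be compared using repeated measures ANOVA". FIM efficiency and length of stay are "compared between groups using ANOVA controlling for the same variables as the primary outcome".

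**Randomisation.** Under Baseline and Randomization in Section XI, "subjects will be randomized (50:50) using a 2-level stratification design based on two pieces of information": centre (three sites) and DelRS-R98 item 1. The levels given are "The rating for the Delirium Rating Scale Item 1 are: 1=Mild, 2=Moderate, 3=Severe". Section X.B says the rating serves at randomisation to control for sleep disturbance severity. No section carries either factor into an analysis model. Demographics as listed in Section X.A do not include centre, and injury severity is not a sleep rating.

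**Baseline data.** The watch is fitted on Days 0-1, randomisation is on Day 2 and light starts on Day 3. A pre-treatment sleep efficiency is therefore available for each patient with usable recordings.

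**The concern.** The baseline value of the outcome is often its best predictor, and it is already being measured. A change score uses it with a slope fixed at 1, and a post-value analysis ignores it. ANCOVA estimates the slope from the data. The strata were judged important enough to balance, but they are not in the model.

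The trial is limited to 128 completers from three sites over three years, so precision given up in the primary comparison cannot easily be regained. The undefined outcome variable adds to this, because an analyst could choose either form after seeing the data.

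**Working it through.** **Inputs from the documents (Section VII).** Effect size 0.5, power 80%, 128 completers, 64 per group. Alpha and sidedness are not stated; 0.05 two-sided is assumed.

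**The plan's own figure.** For a two-sample t-test the noncentrality is 0.5 / sqrt(2/64) = 2.83 on 126 df, which gives 80.1% power. N = 128 reproduces with no covariate term. A one-sided 0.05 test would need only about 50 per group, so it does not match.

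**Inputs not in the documents (assumed).** r is the baseline/follow-up correlation: 0.3, 0.5, 0.7. k is baseline SD divided by follow-up SD: 0.7, 1, 1.25. The documents also do not say whether d = 0.5 is in follow-up SD or change SD units, so both are shown.

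**Variances, with follow-up SD = 1.** Change: 1 + k² − 2rk. Post value: 1. ANCOVA: 1 − r².

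Since (1 + k² − 2rk) − (1 − r²) = (k − r)² ≥ 0, ANCOVA is asymptotically never worse than change, and they tie only at r = k. Since 1 − r² ≤ 1, it is never worse than the post value, and they tie only at r = 0. With other covariates in the model, r and k are the values after adjusting for them.

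**No other covariates, k = 1, 64 per arm:**

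| r | Variance: change / ANCOVA | Ratio | Power, d in follow-up SD: change / post / ANCOVA | Power, d in change SD: change / ANCOVA |
|---|---|---|---|---|
| 0.3 | 1.40 / 0.91 | 1.538 | 66 / 80 / 84% | 80 / 94% |
| 0.5 | 1.00 / 0.75 | 1.333 | 80 / 80 / 90% | 80 / 90% |
| 0.7 | 0.60 / 0.51 | 1.176 | 95 / 80 / 98% | 80 / 86% |

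In the last column the standardised effect under ANCOVA is 0.5 × sqrt(ratio) = 0.620, 0.577 and 0.542. To match ANCOVA on 128 patients, a change score needs 128 × ratio = 197, 171 and 151 patients. The post value needs 128 / (1 − r²) = 141, 171 and 251.

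**With the planned covariates (simulation).** There were 128 patients, 3 centres × 3 severity levels, blocks of 4 (assumed; no block size is stated) and four planned covariates in every model. Covariates explain 20% and strata 10% of the variance at both times. Power for r = 0.3 / 0.5 / 0.7, with d in follow-up SD units:

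| Model | Power |
|---|---|
| Change + planned, k = 0.7 | 76 / 88 / 98% |
| Change + planned, k = 1 | 65 / 79 / 95% |
| Change + planned, k = 1.25 | 53 / 69 / 87% |
| Post value + planned | 88 / 88 / 89% |
| Post value + planned + baseline | 88 / 92 / 98% |
| Post value + planned + baseline + strata | 91 / 93 / 98% |

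On the change reading, baseline gains from 0 (r = k = 0.7) to about 34 points (r = 0.3, k = 1.25; the rounded entries differ by 35). On the post-value reading it gains 0 / 4 / 9 points. If d is in change SD units, the planned change model has about 80% throughout, and the gain over the same grid runs from 0 to about 20 points.

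**Strata and type I error** (r = 0.5, k = 1; strata 10-20% and covariates 10-20% of variance). Change + planned: 4.8-5.2%. Post value + planned: 2.5-3.8%. ANCOVA on baseline without strata: 3.8-4.6%. ANCOVA with baseline and strata: 4.9-5.0%.

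**Secondary scales.** With two time points, the group-by-time test of a repeated measures ANOVA is a t-test on change, so the change-score result applies there too.

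**The case against.** **Baseline may already be used.** A reader might infer that the primary analysis ignores baseline. The documents do not support that: the wording in Section XII is naturally read as a change from baseline, which uses baseline with a fixed slope. What stands is that this is not covariate adjustment, that it loses precision unless r = k, and that the text does not settle the reading.

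**The upper end of the gain is one corner.** About 34 points needs r = 0.3, k = 1.25 and d in follow-up SD units, none of which the documents give. In change SD units the ceiling is about 20. The simulation also makes covariate effects stable over time, so at k = 1 they cancel from the change score. If they predicted follow-up only, the gain at r = 0.5 and k = 1 would still be 88% to 97%. This objection bears on size, not direction.

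**Strata are weak support.** They add 0 to 3 points once baseline is in. A reader might infer that omitting them inflates type I error. It does not: the effect is conservatism, and only where the post value is analysed.

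**Actigraphy dates.** Table 1 marks actigraphy to Day 12, while Section XI has the watch worn "from enrollment to outcome measurement". A reader might call this a contradiction, but a watch worn until the Day 13 assessment fits both, since the last night starts on Day 12. What stands is that no section names the nights to be averaged. Table 1's baseline column covers Days 0-2, so a Day 2 night would follow randomisation but precede light. Table 2 lists an actigraphic data handling plan, not included here, which may define them.

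**Aim 2 is exploratory**, so precision matters less for the secondary outcomes. That is fair; the change there is for consistency.

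**Conclusion.** The concern holds as forgone precision together with an undefined primary variable. A reader might go further and infer bias, an invalid test or an underpowered trial. Randomisation keeps the planned contrast unbiased, no scenario examined showed material type I inflation, and 128 reproduces under the plan's own inputs.

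Over the assumed grid the gain from baseline spans nil to substantial, and its size turns on r, k and the units of d. Direction is secure asymptotically; size is not. The strata are a secondary improvement. The change should be made, with medium confidence in how much it will yield.

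**What to change.** In Section XII, define the primary variable as average post-treatment sleep efficiency. Analyse it by ANCOVA with treatment, baseline average sleep efficiency, centre, DelRS-R98 item 1 as coded at randomisation, and the planned covariates at pre-randomisation values. The last condition matters for medication: Section X.A records it during treatment and at outcome as well, and Section XVIII leaves other sleep treatments unblocked, so later values could be affected by the assigned light.

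State which pre-light nights form the baseline average and which nights form the post-treatment average. State the randomisation code for eligible patients rated 0: the exclusion criteria and the appendix checklist admit them if on sleep medication, but Section XI lists levels 1-3 only.

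Use the same baseline-and-strata-adjusted form for the secondary scales, and add the strata to the FIM efficiency and length-of-stay models.

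**Cost.** Wording only, with no new data. The primary model uses 5 more degrees of freedom (baseline 1, centre 2, severity 2), or 6 with a fourth severity level. If the added terms were wholly uninformative, the treatment variance would rise by about 1.2% and power would fall by about 0.5 point (79.1% to 78.6% in simulation).
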